### **6.2.3. Best Response**

Best response will be summarized for the full analysis set.

Best response is derived from the cycle 1 and cycle 2 disease assessments according to the investigator (Section 3.2.3). The summary will include response (CR+CRi), along with the subcategories CR, CRi, and no response.

Best response will be summarized as a binary variable using frequency counts, percentages, and will additionally include a 95% Clopper-Pearson CI for the rate.

Additionally, summaries of the disease assessment for each cycle (Cycle 1 and Cycle 2) summarizing the categories as collected on the CRF with the exception that CR will be used (combining any CRF category with CR in the label). The denominator will include only patients who received that cycle.

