7.5. Response Assessments

Response assessment will be determined as follows:

- Starting with Day 15, blood cell and differential counts will be examined 3 times a week after GO dosing until determination of remission status; subsequently CBC and differential counts will be collected once weekly until EOT visit (ie, 36 days after the last dose of GO), or until start of Cycle 2 (if administered), or until start of subsequent therapy (eg, consolidation and/or conditioning regimen).
- Efficacy evaluation and determination of remission status by blood and bone marrow aspiration (and biopsy if applicable) will be conducted at the end of each cycle after blood count recovery (neutrophils $\geq 500/\mu\text{L}$ and platelet $\geq 50,000/\mu\text{L}$) is observed or at a maximum of 36 days after the last dose of GO regimen.
- A bone marrow aspirate is required to assess response to treatment, and a bone marrow biopsy is also recommended to confirm response and to assess cellularity and is required in case of a dry tap.

The second cycle will be allowed at the investigator's discretion for patients who meet the following dosing criteria after Cycle 1(refer also to [Table 3](#) describing hematologic toxicities):

- Bone marrow with a decrease of blast percentage to at least 25% or a decrease of pretreatment blast percentage by at least 50%; **and**

- Blood count with neutrophils $\geq 1,000/\mu\text{L}$ and platelets $\geq 50,000/\mu\text{L}$, except in patients with the bone marrow blasts $\geq 5\%$, the decrease in neutrophils and platelets thought to be due to the underlying leukemia.

Patients who don't meet these criteria after the first cycle of GO will not be allowed to receive the 2nd cycle.

Response will be assessed using European Leukemia Net (ELN 2017) recommendations (Table 5).⁵

Table 5. European Leukemia Net (ELN 2017) Recommendations⁵

Complete Remission (CR)	
 • Bone marrow blasts $<5\%$; absence of circulating blasts and blasts with Auer rods; absence of extramedullary disease; • ANC $\geq 1 \times 10^9/\text{L}$ (1000/μL); platelet count $\geq 1 \times 10^9/\text{L}$ (100,000/mL).
CR with incomplete hematologic recovery (CRI)	
 • All CR criteria except for residual neutropenia; ANC $< 1 \times 10^9/\text{L}$ (1000/μL); or thrombocytopenia; platelet count $< 1 \times 10^9/\text{L}$ (100,000/mL).

[figure not shown]

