Appendix 4. List of Drugs Known to Predispose to Torsades de Pointes

The medications which are known to be associated with a risk of TdP and known to prolong the QTc interval are listed in the CredibleMeds® TdP risk category (<https://www.crediblemeds.org>).

(CredibleMeds® is associated with University of Arizona Cancer Center for Education and Research on Therapeutics [CERT]: “Torsades List: Drugs with a Risk of Torsades de Pointes,” Advisory Board).

**Appendix 5. Definition of Refractory and Relapsed AML (ELN 2017
Recommendation)⁵**

Refractory Disease:

- No complete remission (CR) or CR with incomplete hematologic recovery (CRi) after 2 courses of intensive induction treatment; excluding patients with death in aplasia or death due to indeterminate cause.

Relapsed Disease:

- After CR without minimal residual disease (CR_{MDR-}), CR, or CRi, bone marrow blasts $\geq 5\%$; or reappearance of blasts in the blood; or development of extramedullary disease.

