##### **3.2.3. Best Response**

Efficacy evaluation and determination of remission status by blood and bone marrow aspiration (and biopsy if applicable) per the investigator will be classified according to European Leukemia Net (ELN 2017) recommendations according to the following categories. Thus the bone marrow will be assessed by the investigator after each cycle when blood count recovery (neutrophils  $\geq 500/\mu L$  and platelet  $\geq 50,000/\mu L$ ) is observed or at a maximum of 36 days after the last dose of GO regimen. The date of response is also dependent on the observation of the peripheral blood recovery mentioned in the criteria below. If Cycle 2 is to be administered, note that the Cycle 1 assessment is required to be conducted prior to the start of Cycle 2.

Response will be defined as CR or CRi which are defined as follows per ELN 2017:

- Complete Remission (CR): Bone marrow blasts < 5%; absence of circulating blasts and blasts with Auer rods; absence of extramedullary disease; ANC  $\geq 1 \times 10^9/L$  (1000/ $\mu$ L); platelet count  $\geq 100 \times 10^9/L$  (100,000/ $\mu$ L)
- CR with incomplete hematologic recovery (CRi): All CR criteria except for residual neutropenia; ANC  $< 1 \times 10^9/L$  (1000/ $\mu$ L); or thrombocytopenia; platelet count  $< 100 \times 10^9/L$  (100,000/ $\mu$ L)

Best response will be derived from the CRF values for the two cycles: as CR if either Cycle 1 or Cycle 2 are CR, or if no CR then if either Cycle 1 or Cycle 2 are CRi the best response is CRi. Patients without a documented CR or CRi will be considered as non-responders.

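### Read literally, the pooling rule for the per-cycle response tables in SAP 6.2.3 puts CRi in the CR row, although the SAP elsewhere keeps the two apart

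*SAP*

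**What the plan says.** SAP 6.2.3 describes two presentations of response.

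- **Best response**, one result per patient, in the full analysis set: "The summary will include response (CR+CRi), along with the subcategories CR, CRi, and no response".
- **Disease assessment by cycle**, added as a further descriptive display: "summaries of the disease assessment for each cycle (Cycle 1 and Cycle 2) summarizing the categories as collected on the CRF". One departure from those categories is then allowed, and it is the rule at issue here: "with the exception that CR will be used (combining any CRF category with CR in the label". On the denominator: "The denominator will include only patients who received that cycle".

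The definitions are in SAP 3.2.3. CR requires both neutrophil and platelet recovery. The second category begins "CR with incomplete hematologic recovery (CRi): All CR criteria except for residual neutropenia" and goes on to cover low platelets. The same section takes best response from the CRF values and ranks the two categories: "if no CR then if either Cycle 1 or Cycle 2 are CRi the best response is CRi". Protocol Section 7.5, Table 5, lists the incomplete category as "CR with incomplete hematologic recovery (CRI".

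**The concern.** The pooling rule works on the text of a label. Since CRi is named as a kind of CR, a rule that collects every label containing CR also collects CRi. The resulting row is headed CR, not CR/CRi.

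CR would then have two meanings within one section: excluding CRi in the best-response table and including it in the per-cycle tables. The two categories differ only in neutrophil and platelet recovery, and the protocol (Section 1.2.2.4) describes delayed recovery as a known effect of the drug. A reader who takes a per-cycle CR percentage at face value would believe that more patients had full count recovery than did. The CRi row of that table would be empty or absent.

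**Working it through.** The documents give no figure that depends on this rule, so there is nothing of the plan's own to reproduce. The check applies the rule to the labels and then sizes the effect.

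**Step 1. Apply the rule to the labels in the documents.**

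| Label | Where | Contains CR? | Row under the rule |
|---|---|---|---|
| Complete Remission (CR) | SAP 3.2.3; Protocol Table 5 | yes | CR |
| CR with incomplete hematologic recovery (CRi) | SAP 3.2.3; Protocol Table 5 | yes | CR |
| CRi | SAP 3.2.3, 6.2.3 | yes | CR |
| CR without minimal residual disease | Protocol Appendix 5 | yes | CR |

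The last label occurs in the definition of relapse ("After CR without minimal residual disease"), not in the response table. It shows the kind of variant the rule may have been written to absorb, but the SAP does not say so.

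**Step 2. Is CRi a CRF value?** Yes. SAP 3.2.3 derives best response from the CRF values and treats CRi as one of them. Its exact wording on the CRF is not known. If the CRF spelled out complete remission with no abbreviation, the rule would fail to select plain CR as well, so that possibility does not make the rule work.

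**Step 3. Size of the shift.** Let N be the patients who received the cycle, a the number with CR and k the number with CRi.

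- CRi kept separate: CR rate = a/N.
- Rule read literally: CR rate = (a + k)/N.
- Difference = k/N, the CRi share. The CR+CRi total, (a + k)/N, is the same either way.

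The documents give no expected CRi rate. With assumed counts and N = 50:

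| a | k | CR, CRi separate | CR, rule as written | Difference |
|---|---|---|---|---|
| 13 | 0 | 13/50 = 26% | 13/50 = 26% | 0 points |
| 13 | 4 | 13/50 = 26% | 17/50 = 34% | 8 points |
| 10 | 8 | 10/50 = 20% | 18/50 = 36% | 16 points |

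For orientation only, the earlier Phase 2 study of the same fractionated regimen (Protocol 1.2.2.4) had 15 CR and 4 CRp among 57 patients: 15/57 = 26.3%, 4/57 = 7.0%, and pooled 19/57 = 33.3%. CRp is not CRi, and those counts are not by cycle.

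**Step 4. What information is lost?** For a patient given only Cycle 1, best response is the Cycle 1 assessment, so the best-response table already shows the split. The loss concerns patients given both cycles. Someone with CRi after Cycle 1 and CR after Cycle 2 would appear as CR in both columns, and best response would also be CR. That sequence can occur under the plan: the Cycle 2 criteria accept platelets from 50,000/µL (SAP 2.2), while CR needs 100,000/µL (SAP 3.2.3).

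**The case against.** The strongest reply is that the rule acts on CRF labels that cannot be seen here, and that its purpose was probably to merge variants of CR. SAP text next to redaction marks may also name the response categories. This stands as a limit on certainty: the mislabelling is what the sentence instructs, not something shown to have happened. It does not rescue the sentence, because every CRi label available contains CR and no exclusion is written.

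The reply is also right that the table is an added descriptive display, with no confidence interval or decision rule specified for it.

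A reader might infer more than the documents support:

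- *That the response endpoint is inflated.* It is not. SAP 3.2.3 derives best response from the CRF values, not from the pooled row, and its Clopper-Pearson interval is unchanged. Reuse of a pooled variable in that derivation would be a programming error that the SAP does not instruct.
- *That the tables would no longer agree with the count-recovery analyses.* They would. Those analyses use responders in each cycle (SAP 6.6.3.1), and a responder has CR or CRi (SAP 3.2.3), so a pooled row describes the same group.
- *That pooling is why the per-cycle and best-response tables do not match.* They use different denominators, and best response takes the better of two cycles, so exact agreement was never expected. The real inconsistency is that CR and CRi are split in one table and not in the other.
- *That a specific overstatement can be expected.* The earlier study's 19 against 15 (19/15 = 1.27) comes from a CRp count in other patients and predicts nothing here.

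**Conclusion.** Wrong as written, and minor. The sentence tells the analyst to report CRi as CR in the Cycle 1 and Cycle 2 tables, against the separate definitions in SAP 3.2.3 and the separate subcategories in the same SAP section. The error in a per-cycle CR percentage equals the CRi share of that cycle and is zero if no patient has CRi.

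This rests on two conditions: at least one patient has CRi, and the CRF label for it contains CR. The second is likely from the labels in both documents but cannot be confirmed without the CRF. The CR+CRi total, best response and its interval, the recovery analyses and the primary QTcF analysis do not depend on this rule.

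**What to change.** In SAP 6.2.3, replace the label-based rule with an explicit mapping:

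- list by name the CRF categories that are merged into CR;
- state that CRi is shown as its own row and is not merged;
- add a CR+CRi row for each cycle.

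If pooling was intended, keep it and head the row CR/CRi. The list should be taken from the CRF itself. CR without minimal residual disease should not be written in on the strength of Protocol Appendix 5, because it is not a response category in Protocol Table 5 or SAP 3.2.3.

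The cost is one sentence in the SAP and the matching line in the programming specification. No new data are needed and no other analysis changes.

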### **6.2.4. Overall Survival**

Overall Survival will be summarized for the full analysis set.

Overall survival is defined as the time from the start date to the date of death due to any cause. Patients last known to be alive as censored at the date of last contact (Section 5.2.6).

Overall survival will be reported in months and derived as ((death date or censoring date) – start date +1)/ 30.4375.

The summary will include the number of deaths as well the cause of death, the number of censored patients as well as the reason for censoring (Withdrawal of consent, Lost to Follow-up, Alive).

Overall survival will be summarized using the Kaplan-Meier method. The quartiles and probabilities of an event at 6 months and 12 months will be estimated by the Kaplan-Meier method. Confidence intervals (95 %) for quartiles will be based on the Brookmeyer-Crowley method. Confidence intervals (95%) for the estimated probability of event at 12 months will be generated using the log(-log) method with back transformation to a confidence interval on the untransformed scale.

The estimated overall survival curves will be displayed graphically, with one graph including estimates for the adult and pediatric patients separately,. Graphs will describe the number of patients at risk over time.

Deaths related to COVID-19 will be presented in listings, if there are < 5 COVID-19 related deaths.

CC1

## 6.4. Subset Analyses

CC1

Time to Recovery as described in Sections 3.5.2.1, 3.5.2.2 and 6.6.3.1 is defined only for responding patients.

Description of HSCT characteristics is provided only for patients with HSCT; refer to Sections 6.5.1.4 and 6.5.5.

## 6.5. Baseline and Other Summaries and Analyses

### 6.5.1. Baseline Summaries

Refer to Section 3.4 for the definition of baseline.

#### 6.5.1.1. Demographic and Physical Characteristics

The following demographic and baseline characteristics will be summarized by number and percentage: (full analysis set)

- Sex (male, female)
- Age according to the categories: (< 12, 12- <18 years, 18- <45; 45- <65;  $\geq$ 65). Age will be derived based on the collected year of birth.
- Race (according to the categories collected on the CRF, if multiple categories were indicated, then the patient will be reported as “Other”)

- Ethnicity (Hispanic or Latino, Not Hispanic or Latino, Not Reported)
- Region (US, Canada, and Europe including also the countries within Europe)
- Eastern Cooperative Oncology Group (ECOG) Performance status (by values 0, 1, 2, etc.).

Age (years, as continuous variable), and Body Surface Area (BSA) ( $\text{m}^2$ ) will be summarized with descriptive statistics (mean, median, standard deviation, minimum, and maximum).

Body Surface Area (BSA) ( $\text{m}^2$ ) will be computed using Du Bois Formula:  $0.007184 \times \text{Weight}(\text{kg})^{0.425} \times \text{Height}(\text{cm})^{0.725}$

#### 6.5.1.2. Disease Characteristics

The following disease and baseline characteristics will be summarized by number and percentage: (full analysis set)

CC [REDACTED]

- Percent CD33 positivity based on local laboratory (0,  $>0 - <30$ , 30 -  $<70$ ,  $\geq 70$ )
- FAB Subtype (according to values collected on the CRF)
- Risk according to the ELN 2017 guidelines (favorable, intermediate, adverse) per the investigator as collected on the CRF.
- Patients with extramedullary disease (EMD) (yes, no derived from baseline assessment of EMD).

Additionally the following variables will be summarized with descriptive statistics (mean, median, standard deviation, minimum, and maximum) (full analysis set)

- Absolute blasts in the peripheral blood ( $10^9/\text{L}$ )
- Percentage of blasts in the bone marrow
- The CCI measures of CD33 expression (percent CD33 positivity CCI [REDACTED])
- Baseline White Blood Cell Count ( $10^9/\text{L}$ )

Time since initial diagnosis (months), defined as (first dose date – date of initial diagnosis)/30.4375, will be summarized by descriptive statistics (mean, median, standard deviation, minimum, and maximum).

Time since onset of current episode (days), defined as (first dose date – date of current diagnosis), will be summarized by descriptive statistics (mean, median, standard deviation, minimum, and maximum).

CCI

#### **6.5.1.3. Medical History**

Medical history will be coded using the most current version of MedDRA and summarized by MedDRA's System Organ Class (SOC) and PT. Each patient will be counted only once within each PT or SOC. Summaries will be ordered by primary SOC and PT in alphabetical order. The summary will include conditions that were recorded as either past or present. (safety analysis set)

#### **6.5.1.4. Prior Anti-Cancer Treatments**

Summaries will be for the full analysis set.

Prior anti-cancer systemic therapies will be identified as therapies with start date prior to the first dose of study treatment.

A summary of the number of prior regimens according to the number and percentage of patients with 1, 2, 3, or  $>3$  induction regimens will be provided.

A summary of the number and percentage of patients with at least one prior regimen, and the number of patients with at least one induction regimen, at least one conditioning regimen, at least one consolidation or intensification regimen, and at least one maintenance regimen).

Prior radiation treatments will be identified by start date prior to the first dose of study treatment. A summary of the number and percentage of patients with at least one prior radiation treatment given for conditioning, and the number and percentage of patients with at least one prior radiation treatment for other reasons will be provided.

Prior HSCT will be identified by start date prior to the first dose of study treatment. The number and percentage of patients with at least one prior HSCT and a summary of patients according to the number of prior HSCT (1,  $>1$ ) (number and percentage) will be provided. Prior HSCT will be identified by HSCT date prior to the first dose of study treatment. If a patient has more than one prior HSCT, then the last HSCT prior to study treatment will be included in the summary.

For the patients with a prior HSCT, a summary of the following characteristics (number and percentage) using patients with a prior HSCT as the denominator will be provided. Each of the following aspects will be summarized according to the categories collected on the CRF.

- Time of transplant relative to first GO dose (<2 mos or  $\geq$ 2 mos before the first dose of GO)
- Type of transplant
- Donor relatedness
- HLA compatibility
- Stem Cell Source
- Type of conditioning
- Disease Risk at Transplant

#### 6.5.2. Study Conduct and Subject Disposition

**Evaluation Groups:** A summary of the number of patients screened, the number of screen failures, the number of patients enrolled, and the number treated and not treated with percentages for the last two items based on the number of patients enrolled. Additionally, the number of patients in each analysis set will be summarized.

**Protocol Deviations:** Protocol deviations will be compiled prior to database closure and categories will be assigned by the study clinician. Potentially important protocol deviations will be summarized by category (number and percent) (full analysis set). As relevant, important protocol deviations due to COVID-19 will be included. Protocol deviations related to COVID-19 will be presented in listings.

**Disposition:** Disposition events will be summarized for each phase (screening, treatment, and follow-up (representing end of study)) with number and percentage. Within a phase, a summary of the reason for discontinuation as collected on the CRF, and the number completed that phase. (full analysis set) Discontinuations related to COVID-19 will be presented in a separate summary table.

**Inclusion and Exclusion Criteria:** The number and percentage of patients who did not meet at least one of these criteria will be summarized. Additionally, the number and percentage of patients who did not meet each criterion will be summarized. (full analysis set and screen failure patients)

**Impact of COVID-19 on Missed ECG Assessments:** Impact to Cycle 1 ECG assessments will be assessed by showing assessments completed before and after the anchor date (Section 5.2.14) and planned assessments (relative to the first dose date).

#### 6.5.3. Study Treatment Exposure

Study treatment exposure (GO dosing) will be summarized for the safety analysis set.

The following will be summarized with frequencies and percentages for each cycle:

- Patients receiving each dose (GO on Day 1, Day 4, Day 7) according to nominal timepoint.
- Patients receiving all doses in the cycle.
- Duration of treatment of GO computed from the first dose to the last dose within the cycle and categorized as <7 days, 7 days, >7 days.

For patients receiving Cycle 2, the study day for the start (first GO dose) in Cycle 2 categorized as Before Day 28, Day 28 to Day 34, Day 35 to Day 42, Day 43 to Day 49, After Day 50 will be summarized with number and percentage.

Exposure including all cycles received in terms of total number GO doses categorized as <3, 3, 4, 5, 6 doses which will be summarized with number and percentage.

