5.4.3. Dosage Modification for Toxicities

- Every effort should be made to administer study medication on the planned dose and schedule. Patients are to be instructed to notify investigators at the first occurrence of any adverse symptom. In the event of multiple toxicities, dose modification should be based on the worst toxicity observed.
- Full recovery from hematologic toxicities is not a requirement for administration of the second or third dose on Day 4 or 7, respectively.

- In the event of non-hematologic toxicities, dosing may be delayed, omitted or discontinued as described below (Table 3) by monitoring chemistries especially total bilirubin, AST, ALT, and other severe or life-threatening non-hematologic toxicities through recovery from treatment-related toxicities.
- In the event of persistent hematologic toxicities after Cycle 1, conditional Cycle 2 dosing may be delayed or discontinued as described below (Table 3) by monitoring blood counts through recovery from treatment-related toxicities.

Table 3. Dosage Modifications for Non hematologic and Hematologic Toxicities

Non-hematologic Toxicities	Recommended Actions
VOD/SOS	
 • Discontinue GO.
Total bilirubin greater than $2 \times$ ULN, or AST and/or ALT greater than $2.5 \times$ ULN	
 • Delay treatment with GO until recovery of total bilirubin to less than or equal to $2 \times$ upper normal limit (ULN) and AST and ALT to less than or equal to $2.5 \times$ ULN prior to each dose. • Omit scheduled dose if delayed more than 2 days between sequential infusions.
Infusion-related reactions	
 • Interrupt the infusion and institute appropriate medical management. • Administer acetaminophen, diphenhydramine and/or methylprednisolone, if needed. • Provide supportive care measures as needed. • For mild, moderate or severe infusion related reactions, once symptoms resolve, consider resuming the infusion at no more than half the rate at which the reaction occurred. Repeat the procedure above in the event of recurrence of symptoms. • Permanently discontinue GO upon occurrence of a severe infusion reaction or for any life-threatening infusion reaction.

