6.2. Study Period

The total study period at each cycle is comprised of following periods:

- GO Treatment: Starts with the first dose of GO (Day 1) and ends with the last dose of GO (usually Day 7).
- Post-GO Period: Starts on the day after the last dose of GO and ends on 36 days after the last dose of GO or start of subsequent anticancer therapy, including consolidation and/or conditioning regimen. This period ends with End-of-Treatment (EOT) visit.
- If the optional second cycle of GO is administered, the same GO Treatment and Post-GO Periods are repeated starting once when Cycle 1 remission status is determined. The second cycle must be started no later than 42 days after the last dose of GO. This period ends with End-of-Treatment (EOT) visit.
- Follow-up Period: Starts on the day after EOT visit and ends when a patient completes 12 months on the study or death, whichever occurs first. This is end of study for each patient.

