6.2.1. GO Treatment

Each cycle includes an active GO treatment phase (Days 1, 4, and 7) and a post GO treatment phase (Day 10 to 21).

The second cycle is allowed at the investigator's discretion for patients who meet the following dosing criteria after Cycle 1 (refer also to [Table 3](#) describing hematologic toxicities): Bone marrow with a decrease of blast percentage to at least 25%, or a decrease of pretreatment blast percentage by at least 50%; **and** blood count with neutrophils $\geq 1,000/\mu\text{L}$ and platelets $\geq 50,000/\mu\text{L}$, except in patients with the bone marrow blasts $\geq 5\%$, the decrease in neutrophils and platelets thought to be due to the underlying leukemia.

Patients who don't meet these criteria after the first cycle of GO are not allowed to receive the 2nd cycle. Cycle 2 Day 1 must be started no later than 42 days after the last dose of GO (ie, Cycle 1 Day 7).

6.2.2. Cycle 1

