### **5.2.3. Definition of Study Day**

The study day for assessments occurring on or after the first dose of study treatment (e.g., adverse event start date) will be calculated as:

Study day = Date of the assessment/event - start date of study treatment + 1.

The study day for assessments occurring prior to the first dose of study treatment (e.g., baseline characteristics, medical history) will be negative and calculated as:

Study day = Date of the assessment/event –start date of study treatment.

The study day will be displayed in all relevant data listings.

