### **5.2.4. Definition of Cycle and Cycle Day**

For Cycle 1 and Cycle 2 the actual start date for each patient will be determined from the first start date of dosing from the respective CRF exposure page with a dose recorded.

If Cycle 2 is administered, then the actual stop date for Cycle 1 will be calculated as the start date of Cycle 2 minus one day.

For the last Cycle, actual stop date will be calculated as the minimum of the last dose + 36 and the start date of subsequent anticancer therapy.

The cycle day will be calculated as Cycle day = Date of the assessment/event – cycle start date + 1.

The cycle day will be displayed in all relevant data listings.

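### The SAP's Cycle 2 start categories leave out study Day 50, and because they count from first dose they cannot by themselves show which starts met the protocol's 42-day limit

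*SAP*

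**What the plan says.** For patients who receive Cycle 2, SAP Section 6.5.3 tabulates the study day of the first Cycle 2 dose in five categories: "Before Day 28, Day 28 to Day 34, Day 35 to Day 42, Day 43 to Day 49, After Day 50". SAP Section 5.2.3 sets the clock: "Study day = Date of the assessment/event - start date of study treatment + 1". The first GO dose is therefore Day 1.

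The protocol's limit runs from a different date. Section 6.2.1 says: "Cycle 2 Day 1 must be started no later than 42 days after the last dose of GO (ie, Cycle 1 Day 7" (closing bracket cut). The same sentence, with the same bracketed gloss, stands in footnote 2 to Table 1 and in Section 6.2.3. Section 6.2 gives the limit without the gloss: "The second cycle must be started no later than 42 days after the last dose of GO". Table 3 in Section 5.4.3 uses the same 42-day window from the last first-cycle dose for platelet and neutrophil recovery, also without the gloss.

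Both documents expect that the last Cycle 1 dose may not fall on Day 7. Protocol Section 6.2 says that the GO treatment phase "ends with the last dose of GO (usually Day 7". For non-hematologic toxicity, Table 3 allows a delay and then instructs: "Omit scheduled dose if delayed more than 2 days between sequential infusions". SAP Section 6.5.3 itself plans to show the duration of dosing within each cycle "categorized as <7 days, 7 days, >7 days".

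**The concern.** A categorical summary of everyone who received Cycle 2 should give each patient exactly one category. This one has a gap at Day 50, and the gap sits immediately after the day on which the protocol's limit falls for a patient dosed on schedule. Programmed as written, a Day 50 start is not missing data but belongs to no row, so the rows would not add up to the number who received Cycle 2.

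The second problem is the clock. A reader will naturally use this table to see how Cycle 2 timing compared with the 42-day limit. Days from first dose can be translated into days from last dose only if the last-dose day is known, and the table does not carry it.

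The third is the protocol's gloss. If the Day 7 dose is omitted, the last dose and Cycle 1 Day 7 are not the same date, and the documents do not say which one starts the 42 days.

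**Working it through.** **Inputs.** Study-day definition: SAP 5.2.3. Categories: SAP 6.5.3. Limit of 42 days: protocol 6.2, 6.2.1, 6.2.3 and footnote 2 to Table 1. Scope for delay or omission of a dose: protocol Table 3.

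**Step 1: reproduce the category edge.** Limit as a study day = study day of last Cycle 1 dose + 42. For a Day 7 last dose, 7 + 42 = Day 49. That matches the upper edge of the fourth category.

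**Step 2: check coverage.** The categories cover days up to 27, 28–34, 35–42, 43–49, and 51 onward. Going through every study day from Day 8 to Day 79, the only one without a category is Day 50. For a Day 7 last dose, the first day past the limit is 49 + 1 = Day 50.

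**Step 3: vary the last-dose day, with the limit counted from the actual last dose.**

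| Last Cycle 1 dose | How it can arise | Limit (last dose + 42) | What the table does |
|---|---|---|---|
| Day 4 | Day 7 dose omitted | Day 46 | Days 47–49 are past the limit but share a category with Days 43–46 |
| Day 7 | On schedule | Day 49 | Day 50, the first day past the limit, has no category |
| Day 8 | Third dose 1 day late | Day 50 | Day 50 is within the limit but has no category |
| Day 9 | Third dose 2 days late | Day 51 | Day 50 is within the limit but has no category; Day 51 is within it but shares the last category with later starts |

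Two more extreme cases depend on further assumptions. A last dose on Day 1 gives Day 43, but protocol Section 6.3 lists a second dose held more than 2 days for related non-hematologic toxicity as a possible reason to stop treatment, so such a patient may never reach Cycle 2. A last dose on Day 11 gives Day 53, but only if both dosing intervals may each be extended by 2 days; if delay is counted from the scheduled day, the latest is Day 9.

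**Step 4: compare the glossed and unglossed limits.** With the Day 7 dose omitted and Day 4 the last dose, the unglossed wording gives 4 + 42 = Day 46, and Cycle 1 Day 7 gives 7 + 42 = Day 49, a difference of 3 days. For a third dose given on Day 8 or Day 9, the two differ (Day 50 or 51 versus Day 49) only if Cycle 1 Day 7 means the calendar day. If it names the third scheduled dose whenever given, they agree.

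**Step 5: test the simple repair.** With a last category of Day 50 or later, every day has a category, and for patients last dosed on Day 7 that category holds exactly the starts past the limit. For the other rows above, study day alone still mixes the two groups.

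**The case against.** A reader might infer that late Cycle 2 starts cannot be identified in this trial. The documents do not support that. Cycle starts come from recorded dosing (SAP 5.2.4: "the actual start date for each patient will be determined from the first start date of dosing from the respective CRF exposure page"), and Section 6.5.3 already needs the last dose date within each cycle to compute duration, so the interval can be derived for every patient. Study day and cycle day appear in the relevant listings, and SAP 6.5.2 plans a summary of important protocol deviations. This objection stands, with one reservation: calling a start late in the deviation summary still requires knowing which anchor applies.

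A reader might also say that the table misfiles late starts as on time. It does not: it labels no category on time or late and is presented as an exposure summary, not a compliance test. What remains is that the table alone cannot answer that question.

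Nor does the protocol set two rival deadlines. Every statement of the limit names the last dose; some add a gloss that is right for the usual schedule. The conflict is certain only when the Day 7 dose is omitted.

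Finally, a programmer would probably put Day 50 in the last category without being told. That may be so, but the first category, before Day 28, is followed by one that starts at Day 28. Read the same way, the last category excludes Day 50.

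**Conclusion.** The point holds as a minor defect of one descriptive table, with a related wording point in the protocol. The Day 50 gap needs no assumption beyond a literal reading of the categories. The inability to separate starts within and beyond 42 days rests on counting from the actual last dose, and it affects only patients who receive Cycle 2 and whose last Cycle 1 dose was not on Day 7. If the limit were fixed to calendar Day 7, it would be Day 49 for everyone and closing the gap would be enough. The protocol discrepancy is 3 days (Day 46 versus Day 49) when Day 7 is omitted after a Day 4 dose.

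The documents give no expected number of Cycle 2 patients or of omitted or delayed doses, so the effect cannot be put in patients. No endpoint, analysis set or decision rule uses these categories, and the primary QTcF model uses Cycle 1 data only (SAP 6.1.1).

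**What to change.** In SAP 6.5.3, change the last category to Day 50 or later. Add a tabulation of days from the last Cycle 1 dose to the first Cycle 2 dose, in contiguous categories with a cut at the protocol's own 42 days (for example up to 21, 22–28, 29–35, 36–42, more than 42), using whichever anchor the protocol settles on.

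In the protocol, reconcile the bracketed gloss in footnote 2 to Table 1 and in Sections 6.2.1 and 6.2.3 with the unglossed wording in Section 6.2 and Table 3, at least for patients whose Day 7 dose is omitted. No view is taken here on which anchor is right.

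The cost is a phrase and one added tabulation in the SAP, plus a short protocol clarification. The dose dates are already collected, so no new data are needed.
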